ongoing care management). The latter (clinical data) will be managed using all the protocols that one would normally use with respect to usual clinical care and information protection procedures. Confidentiality with respect to research-obtained data will be protected using a logbook containing each participant's unique identification number, name, and status. This logbook will be maintained at the data management center of the Indiana University Center for Aging Research. The unique identifier will be kept separate from subject identifiers and will be stored with a unique but otherwise meaningless identification number. All data will be double keyed by a data-entry professional. All telephone-acquired data gathered by computer-assisted telephone interviewing (CATI) will be automatically entered in a data secure method and double keying will not be necessary due to immediate and error free method of data entry. In addition, for those in care management the principal investigators will have the opportunity for feedback from the patient and the clinic staff to discuss any problems encountered during the data collection.

M. Reporting of Unanticipated Problems & Adverse Events

A data safety monitoring board (**DSMB**) will be established and will include Drs. [name] (a neurologist), [name] (a geriatrician), [name] (a geriatric psychiatrist), and a biostatistician (TBN). The DSMB will be chaired by [name]. The committee will meet at the Indiana University Center for Aging Research prior to the first patient enrollment to determine the nature of the DSMB report, after enrollment of the first 1000 patients and every six months to evaluate safety measures including overall adverse effects related to the study (including the potential harms from screening such as anxiety, depression), serious adverse events, and death after enrollment into the study. In our study an adverse event will be defined as any untoward medical occurrence in a subject who received study intervention without regard to the possibility of a causal relationship. Adverse events will be collected after the subject has started to receive study intervention. If a subject experiences an adverse event after screening

for the study but prior to randomization, the event will be reported as not related to the study intervention. During the study, study personnel will note any change in the condition(s) and/or the occurrence and nature of any adverse events.

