All adverse events occurring after entry into the study and until study completion will be recorded. An adverse event that later meets the criteria for a serious adverse event (SAE), between study enrollment and completion, will be reported to the local IRB as an SAE. All of the above safety data will be monitored throughout the course of the study in blinded fashion. If a death or clinical adverse event is deemed serious, unexpected, and possibly related to study intervention, the DSMB will be notified immediately to determine the appropriate action to take within the context of the event regarding blinding and reporting. Only the DSMB members will be unblinded in order to preserve the integrity of the data collected during this trial and minimize any potential for bias yet provide appropriate safety monitoring.

Potential benefits of the proposed research to the subjects and others

Although our study is collecting data to identify the benefits and harms of dementia screening among older adults attending primary care clinics, we anticipate some immediate benefit to participants at the stage of the research project following the screening results which may include assurance of a negative screening result or comprehensive assessment and management of positive screening results. Early recognition of dementia will lead to early enrollment in a multi-component dementia care management program that would improve the quality of care for dementia, reduce the burden of informal caregivers, and reduce acute care utilization.

Importance of the knowledge to be gained

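### Section M is inconsistent about whose adverse events are collected and from when; if its own definition is applied, the no-screening arm falls outside adverse event reporting

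*Combined protocol and SAP*

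**What the plan says.** The first paragraph of section M sets the definition: "an adverse event will be defined as any untoward medical occurrence in a subject who received study intervention", whether or not a causal link is possible. The start point comes next: "Adverse events will be collected after the subject has started to receive study intervention". The sentence after that deals with an event occurring after screening for the study but "prior to randomization, the event will be reported as not related to the study intervention". Earlier in the same paragraph, the DSMB is to evaluate adverse effects related to the study, with anxiety and depression named as potential harms of screening, and also "serious adverse events, and death after enrollment into the study".

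The second paragraph uses a different window: "All adverse events occurring after entry into the study and until study completion will be recorded". The rule on expedited reporting begins "An adverse event that later meets the criteria for a serious adverse event (SAE), between study enrollment and completion". On blinding it says "All of the above safety data will be monitored throughout the course of the study in blinded fashion" and "Only the DSMB members will be unblinded in order to preserve the integrity of the data collected during this trial".

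Section M does not say what the study intervention is. Section G (Randomization) speaks of clinics treating both intervention and usual care patients. Section H (Care Processes) names the control and intervention groups separately. Section E (The Usual Care Control Groups) has the 2,000 no-screening subjects continue on usual care.

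**The concern.** The trial exists to weigh the harms of screening against its benefits. Its subjects are 65 or older, and section L states that most have several comorbid conditions. Untoward medical events will be common in such people whether or not they are screened. Because section M counts events regardless of cause, the counts can be interpreted only against the same counts in the other arm.

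A definition tied to receipt of the intervention works against that. Staff who follow the first paragraph would log events in the screening arm only; staff who follow the second would log them in both. If practice differed between staff or clinics, the DSMB would receive totals whose denominator is unclear. At worst, it would have screening-arm adverse events and nothing to set beside them.

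**Working it through.** The plan gives no figure to reproduce here, so the check is a comparison of texts plus one count.

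**Step 1: compare the rules in section M.**

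| Rule | Whose events | From when |
|---|---|---|
| Definition, first paragraph | Subjects who received the intervention | Not stated |
| Collection sentence, first paragraph | Same | Start of the intervention |
| Pre-randomisation sentence, first paragraph | Subjects screened for the study | Before randomisation |
| Recording sentence, second paragraph | No restriction | Study entry to completion |
| SAE sentence, second paragraph | No arm restriction of its own | Enrollment to completion |

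The second and third rows conflict directly: before randomisation nobody has received the intervention, so under the definition there is no adverse event to report. The second and fourth rows give different start points. The first and fourth rows give different populations unless the definition is carried forward into the second paragraph. If it is carried forward, the population conflict narrows, but the loss of the control arm becomes firmer.

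**Step 2: decide whether a control subject can have received the study intervention.** The objective defines the control condition as having no cognitive screener, and sections G and H use intervention in contrast to usual care or control. On that usage a no-screening subject has not received it.

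**Step 3: count.** Inputs from section E: 4,000 enrolled, allocation 1:1.

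- No-screening arm: 4,000 × 1/2 = 2,000.
- Share of enrolled subjects outside the definition: 2,000 / 4,000 = 50%.
- Under the second paragraph's rule without the definition: 0 of 4,000 outside.

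**Step 4: size the timing conflict.** Section E (Screening Process) places the MIS-T after consent and randomisation to the screening arm. If the intervention includes the screen, the gap between entry and start of intervention in that arm should therefore be short. The documents give no interval.

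**Step 5: trace SAEs.** The second paragraph describes an SAE as an adverse event that later meets further criteria, so the restricted definition could carry over. The first paragraph, however, gives the DSMB SAEs and deaths after enrollment with no arm limit. Excluding control-arm SAEs thus requires one sentence to be read through another and against a third.

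**Step 6: identify what is collected in both arms anyway.** PHQ-9 and GAD-7 are compared between arms (section I, Secondary Aim 1). Hospital and emergency episodes come from the health information exchange for all 4,000 (Overview of Data Sources; section H, Health Care Utilization). Deaths after enrollment go to the DSMB. What remains exposed is mainly non-fatal events that do not lead to hospital. The documents give no rate for these, so no event count is estimated.

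**The case against.** The strongest reply is that section M, read as a whole, intends both arms. The second paragraph records all events after entry. Blinded monitoring with only the DSMB unblinded makes little sense if every event comes from one arm. Study personnel are to note changes in condition during the study, with no arm limit, and the DSMB is to settle the form of its report before the first enrollment. The statistical plan contains no adverse event analysis. All of this stands as evidence of intent, and it lowers the severity. It does not remove the restricted definition and start point, which are what staff would use to decide what to log. The DSMB can choose its tables but cannot tabulate events that were not collected.

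It could also be said that the lifestyle questionnaire given to both arms is part of the intervention. The wording of section E is against this: it treats that form as a control questionnaire.

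A reader might infer three stronger points, which the documents do not support.

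- **That study intervention means the collaborative care program alone**, so that only the 100 to 200 subjects expected to be assessed or managed are covered. Section H does use intervention of that program, but section M itself names harms from screening among the effects to be evaluated, so its intervention at least includes the screen.
- **That SAEs plainly have no comparator.** Step 5 shows that this is an inference, opposed by the DSMB clause.
- **That the trial cannot compare harms.** The principal harm scales, deaths and acute care use cover both arms.

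**Conclusion.** The inconsistency is real and lies in the text. Section M gives incompatible start points, and a definition that its next paragraph does not respect. Applied as written, the definition leaves 2,000 of 4,000 subjects (50%) outside adverse event reporting, and the all-cause counts then have no usual-care comparator. This rests on two assumptions: that staff follow the first paragraph rather than the second, and that intervention carries the sense it has in sections G and H. The probable intent was to cover both arms, so the no-comparator outcome is a risk of the wording and not an established feature of the trial.

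The damage is confined to reported adverse events, mainly non-fatal and outside hospital; SAEs are touched only by inference. The hypotheses, the power calculation and the primary outcome are not affected. Severity is minor to moderate: worth correcting because the trial is about harms and the correction is cheap.

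**What to change.** Reconcile the two paragraphs of section M as follows.

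1. Define an adverse event as any untoward medical occurrence in any enrolled, randomised subject, in either arm.
2. Use one window, from study entry to study completion, and state whether entry means consent or randomisation. Align the pre-randomisation sentence with that choice.
3. Delete the sentence that starts collection at receipt of the intervention.
4. Define study intervention once, as including the screen, and use it only for judging relatedness.
5. Record events noted by study personnel at the existing interviews in the same way in both arms.
6. List separately the events that reach the study only through the care program, because only screening-arm patients can generate them.

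The cost is a change of wording and some event logging in the control arm. The listed survey instruments contain no adverse event item, so this fix makes capture at interview the same in both arms but not exhaustive. A dedicated question is not required for it. If one were added at 1, 6 and 12 months, it would apply to at most 4,000 × 3 = 12,000 interviews. It would also need consent and IRB wording, since section L bars additional data collection without both.

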[figure not shown]

written materials to assist in caregiver education and support.

Through this summary of our preliminary studies we hope to establish our preparedness for the successful completion of this pragmatic clinical trial of dementia screening in primary care.

E. CHOICE Trial

We are proposing to enroll 4,000 adults, aged 65 and older, attending 10 primary care clinics in Indianapolis; these clinics are representative of two large health care systems: Wishard Health Services (WHS) and IU Health (IUH). We will randomize older adults at ratio of 1:1 into “no screening” or “screening” groups. Subjects randomized into the screening group who have a positive screening would be further referred into a dementia diagnostic assessment and counseling and management program. Our outcomes will be measured at baseline, 1, 6 and 12 months. Using data from our local Regional Health Information Exchange, the Indiana Network for Patient Care (INPC), we will collect health care utilization data of our samples; and monitor new diagnosis, diagnostic testing, and prescribed treatments and referrals. The flow diagram for the proposed study is depicted below.

Subject Recruitment

Established in 1999, the Indiana University Practice Based Research Network (IU-PBRN) consists of 17 primary care centers affiliated with Wishard Health Services and Indiana University Health.⁷³ These two systems serve a diverse population of insured and uninsured patients throughout Indianapolis. More than 110 primary-care physicians practice at these sites. These physicians treat approximately 100,000 patients per year in more than 300,000 visits annually. Using the INPC data repository, IU-PBRN effectively uses informatics tools to streamline patient recruitment and follow-up.⁷³ Since its inception, the IU-PBRN has screened more than 45,000 primary care patients, enrolling more than 17,000 subjects into more than 75 studies. The study team has been utilizing the IU-PBRN since its inception and the successful completion of these projects, described in the Preliminary Studies section, are a testament to

the effectiveness of the IU-PBRN. The IU-PBRN achieved this success through the following informatics innovations.

Centralized Electronic Data Management:

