home visit interview, the care coordinator travels to and conducts a face-to-face initial assessment at the patient's and/or informal caregiver's residence or preferred location. At the patient's home, the care coordinator conducts a brief cognitive assessment; biopsychosocial needs assessment of patient and informal caregiver, and medication reconciliation. The program uses standardized assessment tools including: The Healthy Aging Brain Care Monitor (HABC-M).¹⁰⁸ If there is no available or identified caregiver, the care coordinator attempts to identify a caregiver and complete the caregiver questions at a later date either by phone or in person. The care coordinator documents the initial and follow up visits using care coordination software called the eMR-ABC.

The Plan of Care Development Phase: This phase is designed to facilitate the creation of an

individualized care plan with an emphasis on coordinating care with the patient's primary care provider. This phase begins after the first home visit and concludes with the second home visit by the care coordinator. After consultation and coordination with the program geriatrician and primary care physician, the care coordinator rules in or out the diagnosis of dementia and its subtypes, and finalizes the individualized care plan with the primary care physician.

Complex patients or patients with diseases that may benefit from specialty care, may be recommended for specialty evaluation and co-management. If necessary, the patient will be referred for a more extensive cognitive

and mental health evaluation at the local memory care practice. This decision would be jointly reached by the program geriatrician ([name]) and the patient's primary care provider. Finally,

Program Services and Protocols

- Self-Management /Caregiver Skills Enhancement
- Support Group Participation
- Informal Telephone Support
- Problem Solving Training
- Reducing Anticholinergic Medications
- Prescribing FDA-Approved Medications
- Managing High Vascular Burden
- Monitoring and Supporting of Caregiver's Emotional and Physical Health
- Managing Transitional Care
- Managing Acute Care Problems
- Root-Cause Analysis of Re-Hospitalization or Re-Emergency Room Visit
- Care Prioritization

the care coordinator will schedule a second face-to-face home visit with the patient and the informal caregiver within 2-4 weeks of the initial home visit.

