The Second Home Visit Phase: The care coordinator discusses the individualized care plan; explains the diagnosis, the natural history, and the prognosis of dementia; implements appropriate care protocols; reviews, explains, and distributes the corresponding educational handouts for both the patient and the informal caregiver; and connects patients and informal caregivers to in-home services and community resources as needed.

The Follow-Up Phase: It includes interaction with the patient or the caregiver via face-to-face home or clinic visit, phone contact, email, fax or mail. The minimum amount of contact during this time will be once monthly for the first three months and once every three months thereafter. During these interactions, the care coordinator will answer any questions generated from previous visits; collect patient and informal caregiver feedback; reconcile medications and review medication adherence; have the informal caregiver complete the HABC Monitor to trigger the use of specific care protocols; and facilitate the informal caregiver's participation in the Support Program. Throughout the duration of the follow-up phase, the team will continue to work with the patient, the informal caregiver, and the patient's primary care provider to monitor, implement, and adjust as necessary the individualized care plan. The program care services and protocols already developed and fields tested include:

1) Self-Management/Caregiver Skills Enhancement: Prior to this second home visit, the care coordinator prepares the various relevant materials to enhance patient self-management or caregiver skills. These materials (the Patient or Caregiver Care Manual) can include: information on legal and financial planning with referrals made to elder law specialists and legal services programs in the community; specific behavioral interventions techniques to help

manage, reduce or avoid patient problem behaviors; and/or coping strategies to ensure the caregivers' emotional and physical health remain intact. These materials are provided to the patient or the caregiver via various face-to-face or home counseling sessions. If the patient's or caregiver's needs are particularly complex, the counseling can take place over more than one face-to-face and/or telephone sessions.

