year. INPC also carries data from the Marion County Health Department; the Indiana State Department of Health; Indiana Medicaid; and RxHub, a national consortium of pharmacy benefit managers.⁴⁹ The INPC's rich clinical repository is organized by patient and medical record data and segregated into separate files by institutional source, but the data about one patient from many institutions can be viewed as a single virtual medical record, and clinicians can review a patient's record in a variety of video screens and hard-copy formats.

With initial focus in support of quality improvement, INPC is also beginning to serve biomedical research. In a recent clinical trial,^{34,51} we used INPC data to track utilization across the five health care systems in support of analyses examining the impact of new models of care on older adults health care utilization. These data were made available after appropriate approvals from the INPC Privacy Board which includes representative from all five health care systems and the Regenstrief Institute. Our study team has a track record in the responsible use of these data and in their appropriate data management and analysis.

Randomization

We will use a central, computer generated, web-based, randomization scheme to assign individual patients rather than providers or clinics to treatment conditions to minimize the effects of unmeasured case mix differences and clinic-level clustering. We estimate that the risk for 'spillover' from having participating clinics treat both intervention and usual care patients is likely to be small.^{34,51,72} If anything, patient-based randomization will conservatively bias the results in favor of usual care.

H. Data Collection (We will use face-to-face or telephone interviews for our data collections)

Health Related Quality of Life (HRQOL)

The primary outcome measure will be the HRQOL measured at baseline, 1, 6 and 12 months among the entire 4,000 enrollees. We will use the 15-item **Health Utility Index (HUI)** to

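### Section M sets no common schedule or source for adverse events, so extra programme contacts in one arm may inflate the screening arm's counts

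*Combined protocol and SAP*

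**What the plan says.** Section M describes collection in one sentence: "During the study, study personnel will note any change in the condition(s) and/or the occurrence and nature of any adverse events". No visit schedule, scripted question, recall period or list of sources follows.

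Section M also makes two statements on whose events count. The first is that "an adverse event will be defined as any untoward medical occurrence in a subject who received study intervention", together with "Adverse events will be collected after the subject has started to receive study intervention". The second, in the next paragraph, is "All adverse events occurring after entry into the study and until study completion will be recorded".

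Study interviews follow the same calendar in both arms. Section H has quality of life "measured at baseline, 1, 6 and 12 months among the entire 4,000 enrollees", and PHQ-9 and GAD-7 are collected at the same times.

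Programme contacts exist only for screen-positive patients who accept assessment. Under The Collaborative Dementia Care Program (Section E) there is an initial home visit, after which "the care coordinator will schedule a second face-to-face home visit" 2 to 4 weeks later. For the follow-up phase: "The minimum amount of contact during this time will be once monthly for the first three months and once every three months thereafter". The same section adds contacts prompted by events: a visit within 72 hours of hospital discharge, calls about acute problems, and a review within a week of re-admission. The 2,000 controls have usual care.

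**The concern.** A count of adverse events depends on how often someone is in a position to learn of them. If one arm contains patients whom staff see or telephone more often, and an event is logged whenever staff hear of it, that arm can show more events at the same true rate. Some programme contacts are also triggered by hospital discharge or re-admission, which are events a safety log should hold.

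Weighing benefit against harm is the trial's stated objective. The DSMB, whose members alone are unblinded, reviews adverse events, serious adverse events and deaths after the first 1,000 patients and every six months. An excess due to detection could be read as harm from screening, or a real excess could be dismissed as a detection effect. Section M gives the DSMB no means of telling the two apart.

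**Working it through.** **1. Size of the group with extra contacts (Section E, Screening Process).** Screen-positives: 0.15 × 2,000 = 300. Accepting assessment: 300 × (1 − 0.33) = 201, which reproduces the plan's figure of about 200. Of these, 100 are expected to have dementia and 100 not. Shares of the screening arm: 100/2,000 = 5% and 200/2,000 = 10%. Subject Recruitment says 100 are managed and the other 100 counselled, so 5% is the nearer reading for the full contact schedule and 10% is an upper case.

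**2. Contacts in 12 months.** Study contacts after baseline: 3 per subject in both arms. The programme start date is not given, so I assumed a first home visit at day 14, 30 or 60 and a second one 14, 21 or 28 days later, then monthly and quarterly contacts at the stated minimum:
- start day 14: days 14, 28, 58, 88, 118, 209, 300
- start day 30: days 30, 51, 81, 111, 141, 232, 323
- start day 60: days 60, 88, 118, 148, 178, 269, 360

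Each gives 7 programme contacts, so 10 against 3. Mean contacts per arm: (3 + 0.05 × 7)/3 = 1.12, or (3 + 0.10 × 7)/3 = 1.23.

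**3. Capture model.** Assume equal true event rates, events spread evenly over 365 days, programme contacts feeding the log, and an event being noted only if a contact follows within *w* days. With study contacts at days 30, 182 and 365, let *c* be the share of days captured for a subject outside the programme and *p* the share for a programme patient. With programme share *s*:

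arm ratio = 1 + *s* × (*p*/*c* − 1)

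For the day-14 start:

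| *w* (days) | *c* | *p* | ratio, *s* = 5% | ratio, *s* = 10% |
|---|---|---|---|---|
| 14 | 44/365 = 0.121 | 135/365 = 0.370 | 1.103 | 1.207 |
| 30 | 92/365 = 0.252 | 238/365 = 0.652 | 1.079 | 1.159 |
| 60 | 152/365 = 0.416 | 328/365 = 0.899 | 1.058 | 1.116 |
| 90 | 212/365 = 0.581 | 365/365 = 1.000 | 1.036 | 1.072 |
| complete recall | 1.000 | 1.000 | 1.000 | 1.000 |

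The day-30 and day-60 starts keep the 12-month ratios within 1.04 to 1.10 (5%) and 1.07 to 1.21 (10%).

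**4. Chance of a spurious excess.** With 2,000 per arm, at most one event per subject and true incidence *I*, the recorded proportions are *Ic* in controls and *I*[(1 − *s*)*c* + *sp*] in the screening arm. Example with start day 30, *w* = 30, *I* = 60%, *s* = 10%: *c* = 92/365 and *p* = 265/365, so 0.151 against 0.180. The standard error is √[(0.151 × 0.849 + 0.180 × 0.820)/2,000] = 0.0117, z = 2.42, and the chance of exceeding 1.96 is 0.68. Over all starts and windows:

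| assumed incidence | *s* = 5% | *s* = 10% |
|---|---|---|
| 10% | 5–7% | 8–15% |
| 60% | 13–23% | 37–68% |

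The nominal upper-tail figure is 2.5%. The incidences are assumptions; the plan gives none.

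**5. Time pattern.** Mean-contact ratio at *s* = 10%, first 91 days against the rest of the year: start day 14 gives 1.40/1 = 1.40 and 2.3/2 = 1.15; start day 60 gives 1.20/1 = 1.20 and 2.5/2 = 1.25. The order reverses.

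**The case against.** The strongest reply is that nothing says programme contacts feed the adverse-event log. Section L separates research data from clinical data obtained in care management, and sends concerns arising there to the primary care provider or emergency personnel. The HABC Monitor is described as a trigger for care protocols, not as a safety source. This stands: feeding is a possibility, not a fact. It does not close the point. The distinction in Section L is drawn in a discussion of confidentiality, Section M asks for all adverse events, and a clinical lead meets the programme nurse weekly. Section M does not say what happens to an event learned that way.

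Second, the harms that the trial names are measured alike in both arms by PHQ-9 and GAD-7, and INPC episodes are extracted for all subjects. This also stands. A reader might infer that the safety data cannot inform the benefit–harm question; that is wrong, because these comparisons do not depend on programme contacts. However, Section M does not tie the DSMB's between-arm rates to these sources.

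Third, the DSMB is to settle the form of its report before enrolment, and no threshold is tied to event counts. True, but the form of a report cannot restore a source that was not recorded.

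A reader might also add 2 + 3 + 3 programme contacts to reach 11 against 3, with six in the first three months and an early peak. The stated intervals do not allow it. Even with the first home visit on day 0 and the second on day 14, contacts fall on days 0, 14, 44, 74, 104, 195 and 286; the next would be day 377. That is at most four programme contacts plus one interview in 91 days, and the early peak depends on the unstated start.

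**Conclusion.** The concern holds as a conditional risk. Section M lacks a common way of ascertaining adverse events, and about 5% to 10% of the screening arm has about 10 contacts against 3. Two conditions are needed for bias: programme contacts feed the log, and recall between interviews is incomplete. Under both, the 12-month arm ratio with no true harm is about 1.04–1.10 (5% share) or 1.07–1.21 (10%). It is 1.00 if either condition fails. Recall windows, start days and incidences are my assumptions. The scheduled contacts are a stated minimum and leave out those prompted by events.

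The documents do not support saying that the DSMB's rates will differ, or that any excess will come early.

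The two statements in Section M on whose events count conflict. Read alone, the first could leave controls with no countable events; the second points the other way. Until they are reconciled, no between-arm rate is well defined. Reconciling them would not by itself equalise detection.

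**What to change.** In Section M:

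1. Base between-arm safety rates for the DSMB on sources identical in both arms: one scripted adverse-event question at the 1-, 6- and 12-month interviews for every subject, the PHQ-9 and GAD-7 scores, and INPC acute-care and, where available, death data over 12 months. For these the ascertainment schedule is the same in both arms by construction.
2. State whether programme contacts feed the log, and record the source of every event.
3. List events learned only through programme contacts separately. Report each one individually, but keep them out of the between-arm rates.
4. Reconcile the definition limited to subjects who received study intervention with the statement covering all events after entry, so that controls' events are counted from the same starting point.

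The cost is revised wording, one source field and one item in interviews already planned; the INPC extraction of acute-care episodes is already planned. The downside is that events between interviews that leave no acute-care record will be recalled less completely, so the common-source rates will be somewhat low in both arms.
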